Title : *A Prospective Randomized Controlled Trial of the Effect of Different Pancreaticojejunostomy After Pancreaticoduodenectomy on Postoperative Pancreatic Fistula Based on the Position of the Pancreatic Duct in Pancreatic Section*

Randomization was generated by a computer program and sealed envelopes labels were opened in the operating room before pancreaticoduodenectomy was performed. The participants were randomly divided into the experimental group and the control group. The experimental group underwent intraoperative measurements (A: short distance from the center of the pancreatic duct to the edge of the pancreas) and (B: pancreatic thickness). When the ratio of the thickness of the short distance from the center of the pancreatic duct to the edge of the pancreas at the pancreatic section was ≥ 0.401 , it was divided into the N1 group (central pancreatic duct). If the ratio was < 0.401 , it was divided into the N2 group (eccentric pancreatic duct). The "central pancreatic duct" group was given "1+1 mode" pancreaticojejunostomy; the "eccentric pancreatic duct" group was given "1+1² mode" pancreaticojejunostomy. The patients in the control group were given "traditional pancreaticojejunostomy".

The sample-size determination was based on the estimate of a previous retrospective study to detect a two-sided difference. Using clinically relevant pancreatic fistula of 23.5% in the control group and 15.8% in experimental group group ($\alpha = 0.05$, power 80%) and the dropout rate was 10%, therefore, it was calculated that 462 patients per arm would be required. Statistical analysis was carried out using SPSS software version 20 (IBM Corp., Armonk, NY, USA). Variables were compared using the χ^2 test and independent samples t-test. Differences were considered significant at a P -value of < 0.05 .

Tests for Two Proportions

Numeric Results for Testing Two Proportions using the Z-Test with Unpooled Variance

H0: P1 - P2 = 0. H1: P1 - P2 = D1 ≠ 0.

Target	Actual						Diff	
Power	Power*	N1	N2	N	P1	P2	D1	Alpha
0.80	0.80085	415	415	830	0.1580	0.2350	-0.0770	0.0500

* Power was computed using the normal approximation method.

References


Fleiss, J. L., Levin, B., and Paik, M.C. 2003. Statistical Methods for Rates and Proportions. Third Edition. John Wiley & Sons. New York.

Lachin, John M. 2000. Biostatistical Methods. John Wiley & Sons. New York.

Ryan, Thomas P. 2013. Sample Size Determination and Power. John Wiley & Sons. Hoboken, New Jersey.

Report Definitions

Target Power is the desired power value (or values) entered in the procedure. Power is the probability of rejecting a false null hypothesis.

Actual Power is the power obtained in this scenario. Because N1 and N2 are discrete, this value is often (slightly) larger than the target power.

N1 and N2 are the number of items sampled from each population.

N is the total sample size, N1 + N2.

P1 is the proportion for Group 1 at which power and sample size calculations are made. This is the treatment or experimental group.

P2 is the proportion for Group 2. This is the standard, reference, or control group.

D1 is the difference P1 - P2 assumed for power and sample size calculations.

Alpha is the probability of rejecting a true null hypothesis.

Summary Statements

Group sample sizes of 415 in group 1 and 415 in group 2 achieve 80.085% power to detect a difference between the group proportions of -0.0770. The proportion in group 1 (the treatment group) is assumed to be 0.2350 under the null hypothesis and 0.1580 under the alternative hypothesis. The proportion in group 2 (the control group) is 0.2350. The test statistic used is the two-sided Z-Test with unpooled variance. The significance level of the test is 0.0500.

Dropout-Inflated Sample Size

Dropout Rate	Sample Size			Dropout-Inflated Enrollment			Expected Number of Dropouts		
	N1	N2	N	N1'	N2'	N'	D1	D2	D
10%	415	415	830	462	462	924	47	47	94

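### The allocation envelope is opened before the resection, although the arms differ only from the cut pancreas onward; open it after transection, once a pancreaticojejunostomy is certain

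*SAP*

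**What the plan says.** The opening paragraph of the SAP fixes when the allocation becomes known: "sealed envelopes labels were opened in the operating room before pancreaticoduodenectomy was performed".

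The same paragraph describes what separates the arms. "The experimental group underwent intraoperative measurements" of the duct-to-edge distance (A) and the pancreatic thickness (B). The ratio that selects the technique uses "the short distance from the center of the pancreatic duct to the edge of the pancreas at the pancreatic section", so it can be obtained only on the cut surface. A ratio of at least 0.401 leads to the 1+1 mode and a lower ratio to the 1+1² mode. Controls receive the traditional pancreaticojejunostomy. No difference between the arms is described for any earlier stage of the operation.

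The second paragraph sizes the trial on clinically relevant pancreatic fistula, 23.5% in controls against "15.8% in experimental group group", and adds that "the dropout rate was 10%, therefore, it was calculated that 462 patients per arm would be required". The table under "Dropout-Inflated Sample Size" gives 47 expected dropouts per arm (94 of 924) without stating a cause.

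**The concern.** Between the opening of the envelope and the point where the treatments diverge lies the whole resection. If the operation changes course in that interval and no pancreaticojejunostomy is made, the patient has been randomised but cannot show the difference under test. Two ways of handling such a patient remain:

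- **Exclusion.** The decision is taken when the arm is already known to the operating team. If knowledge of the arm influences who is left out, the comparison is biased.
- **Counting as a non-event.** This keeps the randomised comparison intact, but both fistula rates shrink by the same factor and so does their difference.

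An analysis set defined in the protocol, which is not shown, can choose between these two but cannot remove both. Opening the envelope later can. At stake are some power and an avoidable opening for selection; the sample-size calculation itself is not in question.

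**Working it through.** **Inputs from the SAP.** Fistula rates p1 = 0.158 (experimental) and p2 = 0.235 (control); two-sided Z-test with unpooled variance; alpha 0.05; 415 evaluable and 462 enrolled per arm.

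**Assumptions.** f is the share of each arm without a pancreaticojejunostomy. The SAP does not give it, so 0%, 2%, 5% and 10% are used, equal in both arms. The planning rates are taken to apply to patients who do receive an anastomosis.

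**Step 1: reproduce the plan's figures.**

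n = [p1(1−p1) + p2(1−p2)] × (1.960 + 0.842)² / (p2−p1)²
= (0.1330 + 0.1798) × 7.849 / 0.077² = 414.1, rounded up to 415.

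Power = Φ(|p1−p2|/SE − 1.960), with SE = √{[p1(1−p1) + p2(1−p2)]/n}. At n = 415, SE = 0.02745, so 0.077/0.02745 = 2.805 and Φ(0.845) = 0.80085, as in the SAP. Dropout: 415/0.9 = 461.1, rounded up to 462. Both figures reproduce.

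**Step 2: count patients without an anastomosis as non-events.** Replace the rates by 0.158(1−f) and 0.235(1−f). For f = 10% these are 0.1422 and 0.2115, a difference of 0.0693. At n = 462, SE = 0.0250, so 0.0693/0.0250 = 2.772 and Φ(0.812) = 0.792.

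| f | Rates (exp. vs control) | Difference | Power, 462 analysed per arm | Power, 415 analysed per arm | n per arm for 80% power, before dropout |
|---|---|---|---|---|---|
| 0% | 15.8% vs 23.5% | 7.7 points | 84.1% | 80.1% | 415 |
| 2% | 15.5% vs 23.0% | 7.5 points | 83.2% | 79.1% | 425 |
| 5% | 15.0% vs 22.3% | 7.3 points | 81.8% | 77.5% | 442 |
| 10% | 14.2% vs 21.2% | 6.9 points | 79.2% | 74.8% | 472 |

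The 462 column assumes no other loss; power reaches 80% at f = 8.4%. The 415 column assumes that 47 per arm are also lost for other reasons, and it starts with almost no reserve.

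**Step 3: let these patients be part of the 10% dropout.** Then 415 per arm have an anastomosis and are evaluable, and 462f non-events are added. For f = 10%, n = 415 + 46.2 = 461.2, of which 46.2/461.2 = 10.0% are non-events. Power is 79.9%, 79.6% and 79.1% for f = 2%, 5% and 10%, against 80.1% planned.

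**Step 4: exclude them, with no other loss.** 462(1−f), rounded down, leaves 452, 438 and 415 per arm, with power 83.3%, 82.2% and 80.1%. At f = 10% the whole dropout allowance is used. These figures cover the loss of numbers only. The bias from selective exclusion cannot be computed from the SAP.

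**The case against.** The strongest reply is that the size of the problem is entirely assumed. The SAP does not say that any randomised patient fails to reach an anastomosis, and its wording allows the envelope to be opened after exploration, which would bring f close to zero. If f lies within the 10% dropout, step 3 shows a loss of about one point. The lower power column arises only when the full dropout is charged to other causes and f is added on top. Exclusion for a reason unrelated to the arm does not bias the comparison, and nothing in the text shows that the arm influences it. The protocol may contain a rule for these patients. Finally, the text is in the past tense, so the timing may no longer be open to change.

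Most of this stands as a limit on size. The power loss may be small, and no bias has been demonstrated. It does not remove the point. The SAP itself fixes the opening before the resection. Opening after exploration lowers f but does not cover an operation that changes course later. The dropout allowance replaces numbers; it neither prevents selective exclusion nor restores a diluted difference.

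**Conclusion.** The concern holds as a weakness of a stated rule, not as an error of calculation. Allocation is disclosed earlier than the design needs, and a randomised patient without a pancreaticojejunostomy must then be excluded with the arm known or counted as a diluting non-event.

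The effect depends on f, which the SAP does not give. For f up to 10%, equal in both arms and counted as non-events, power runs from 84.1% down to 79.2% if nobody else is lost, and from 80.1% down to 74.8% if the full planned dropout comes on top. If f is part of that dropout, power stays at 79.1% or above. The avoidable share of the planned losses lies anywhere between 0 and 94 of 924 patients. Selection bias is a possibility only. The point should be fixed because the remedy is cheap; confidence in its practical importance is medium.

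**What to change.** Open the envelope after pancreatic transection, once it is confirmed that a pancreaticojejunostomy will be made. This brings f to about zero, and 415 evaluable and 462 enrolled per arm can stay. It needs no extra patients. The cost is that the team learns the technique only at reconstruction.

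A useful addition, on which the main change does not depend, is to record A and B in every patient before the envelope is opened. The ratio is then measured blind to arm and is also known for controls. The drawback is that surgeons of control patients would know the measured duct position before the traditional anastomosis, so some contamination is possible, although the cut surface is visible to them anyway. Leaving controls unmeasured avoids this and keeps the main gain. Stratifying the randomisation at 0.401 is a further option and would need a second series of envelopes.

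If recruitment has already taken place, report by arm every randomised patient who had no pancreaticojejunostomy, and analyse all randomised patients. This removes the exclusion bias but leaves the dilution, which should be stated when the result is interpreted.

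### Does bundling new anastomosis modes with a duct-position rule in one arm leave the trial unable to support its own claim?

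*SAP*

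**What the plan says.** The title announces a trial of the "Effect of Different Pancreaticojejunostomy After Pancreaticoduodenectomy on Postoperative Pancreatic Fistula Based on the Position of the Pancreatic Duct in Pancreatic Section".

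The SAP's opening paragraph describes a two-arm randomisation: "The participants were randomly divided into the experimental group and the control group". It then states that "The experimental group underwent intraoperative measurements", namely the short distance from duct centre to pancreatic edge and the pancreatic thickness. A ratio of at least 0.401 puts the patient in the central-duct group, who receive the 1+1 mode. A lower ratio puts the patient in the eccentric-duct group, who receive the 1+1² mode. For the other arm, "The patients in the control group were given" the traditional pancreaticojejunostomy. No measurement or selection is described for controls.

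The sample-size paragraph takes clinically relevant fistula rates of 23.5% (control) and 15.8% (experimental). The Tests for Two Proportions output states the null hypothesis P1 − P2 = 0. Report Definitions identifies P1 with the experimental group and P2 with the control group. The result is 415 evaluable per arm, raised to 462 for 10% dropout.

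**The concern.** Two things differ between the arms at once: the way the anastomosis is made, and the use of a duct-position rule to choose it. No patients receive a new mode without the rule, and no patients with the same duct position are randomised between 1+1 and 1+1². If the new modes simply worked better in everyone, the trial would show the same benefit as if tailoring were the active ingredient.

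Because the title puts duct position in the foreground, a reader could take a significant result as proof that the 0.401 cut-off is useful. The comparison does not test that. At stake would be a wrong conclusion drawn from a correctly executed analysis.

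**Working it through.** **1. Which comparison do the plan's figures belong to?**

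Inputs, all from the SAP: p1 = 0.158, p2 = 0.235, two-sided alpha 0.05, power 80%, Z-test with unpooled variance, 10% dropout.

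- Variance sum: 0.158 × 0.842 + 0.235 × 0.765 = 0.133036 + 0.179775 = 0.312811.
- n per arm = (1.960 + 0.842)² × 0.312811 / 0.077² = 414.1, rounded up to 415.
- Power at 415: SE = √(0.312811 / 415) = 0.02746. Then 0.077 / 0.02746 − 1.960 = 0.845, which gives 0.80085.
- Enrolment: 415 / 0.90 = 461.1, rounded up to 462.

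All three figures reproduce. They size one contrast: everyone in the experimental arm against everyone in the control arm. The SAP states no sample size or power for central against eccentric ducts, or for 1+1 against 1+1².

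**2. Can that contrast separate technique from selection?**

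Let a share f of the 7.7 points come from technique and 1 − f from selection. The experimental rate is 0.235 − 0.077f − 0.077(1 − f) = 0.158 for every f. Overall rates and power are the same throughout, so the design cannot split the effect. This is true of any package compared with a standard, and it does not favour technique over tailoring as the explanation: two modes each well matched to its duct type could also produce a uniform benefit.

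**3. Does the plan need to separate them?**

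Set the title beside the interventions. The title names different forms of pancreaticojejunostomy as the thing whose effect is studied, and duct position as the basis for using them. The experimental arm does that: measure, classify, choose the mode. The power output compares that arm with the control arm. The three agree, and no sentence credits a benefit to the duct-position rule itself.

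Isolating the rule would be a different trial, with a comparator receiving the new modes without selection. As an illustration only (the SAP gives no split), the usual pooled-variance formula for 80% power gives:

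| Assumed technique share f | Fistula rate without selection | Power at 415 per arm | Evaluable per arm for 80% |
|---|---|---|---|
| 0 | 23.5% | 0.80 | 417 |
| 0.25 | 21.6% | 0.57 | 715 |
| 0.5 | 19.7% | 0.31 | 1,544 |
| 0.75 | 17.7% | 0.11 | 5,910 |

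**4. Would an arm-by-ratio interaction settle it?**

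No. In the experimental arm the mode is fixed by the ratio, so any variation of effect with duct position is mixed with the difference between 1+1 and 1+1². A non-zero interaction would not validate 0.401, and a zero one would not refute it. It would also be weak. If the strata were equal in size (an assumption), the interaction SE is about twice the main-effect SE. Power for a 7.7-point interaction then follows from 2.80 / 2 − 1.96 = −0.56, about 29%. It would also need the ratio in controls, whose measurement this SAP does not describe.

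**The case for a change.** The strongest reply is that the analysis text never says which groups are compared. It names the χ² test and the t-test and stops there, while the SAP defines three groups: central, eccentric and control. The labels N1 and N2 make this worse, since they denote the duct-position groups in the opening paragraph and the two arm sizes in the power output. A reader could therefore test the central group against all controls, which is not a randomised comparison.

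Such a test could mislead badly. Assume, with figures not in the SAP, that half the ducts are central, that control risk is 17% for central and 30% for eccentric ducts (mean 23.5%), and that treatment has no effect. Central experimental patients (about 207) against all 415 controls would show 17% against 23.5%, a spurious 6.5 points. The SE is √(0.17 × 0.83 / 207 + 0.235 × 0.765 / 415) = 0.0334. The ratio 0.065 / 0.0334 is 1.95, so the result would be significant about half the time.

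The warning stands: such subgroup comparisons should carry no causal weight. But the SAP neither states nor sizes one. The reuse of N1 and N2 is untidy, but Report Definitions resolves it by tying the numbered groups to experimental and control. If a formal statement of the primary objective exists, it would commonly sit in the protocol, which is not at hand. What remains is a possible misreading of a future result.

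**Conclusion.** The concern does not hold. It is correct that the arms differ in both technique and selection rule, and that no arm isolates either. That limits interpretation; it does not contradict anything the SAP says or invalidate its analysis. Run as written, the randomised comparison supports a sound conclusion about the duct-position-guided package against traditional anastomosis. Naming that contrast again, or adding a disclaimer, would leave 415, 80.085%, 462 and the test unchanged.

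This rests on two readings: that the title describes a guided strategy, and that the comparison is between whole arms, as the power output defines it. It would need to be reopened if the protocol or trial report claimed that the result validates the 0.401 cut-off or ranks 1+1 against 1+1². The SAP does not describe how the three techniques differ, so the size of the technique change cannot be judged here.

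### Does the 10% dropout allowance mean that 94 randomised patients are discarded and that power as randomised is below 80%?

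*SAP*

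**What the plan says.** The second paragraph of the SAP gives the planning rates: "Using clinically relevant pancreatic fistula of 23.5% in the control group and 15.8% in experimental group group". Under Summary Statements it reports that "Group sample sizes of 415 in group 1 and 415 in group 2 achieve 80.085% power", that "The test statistic used is the two-sided Z-Test with unpooled variance", and that "The significance level of the test is 0.0500".

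The allowance for dropout is in the second paragraph: "the dropout rate was 10%, therefore, it was calculated that 462 patients per arm would be required". The closing table, Dropout-Inflated Sample Size, repeats this as 415 inflated to 462 per arm (830 to 924 in total). Under "Expected Number of Dropouts" it lists 47, 47 and 94.

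On allocation, the first paragraph says that "sealed envelopes labels were opened in the operating room before pancreaticoduodenectomy was performed". On analysis, the SAP says that "Variables were compared using the χ^2 test and independent samples t-test", with significance at P < 0.05. It does not say what a dropout is, which patients form the analysis set, or what happens to a patient who drops out.

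**The concern.** The stated power counts 830 of 924 randomised patients, all at the full assumed rates. The other 94 contribute nothing to it. The envelope is opened before the resection, so a patient can be randomised and then not receive the assigned anastomosis. Put together, these facts can look like a plan to compare completers only.

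Two things would then be at stake. Removing about 10% of patients for reasons that arise after allocation could bias the fistula comparison. If those patients were instead kept in their allocated arm with little or no benefit from the assigned technique, the 7.7-point difference would be diluted and 462 per arm would fall short of 80% power.

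**Working it through.** **Inputs, all from the SAP.** Experimental rate 0.158, control rate 0.235, difference 0.077, two-sided alpha 0.05, target power 80%, unpooled Z-test, dropout 10%.

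**1. The stated sample size and power.**

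- Variance sum: 0.158 × 0.842 + 0.235 × 0.765 = 0.1330 + 0.1798 = 0.3128.
- n per arm = 0.3128 × (1.960 + 0.842)² / 0.077² = 414.1, rounded up to 415.
- Power at 415 = Φ(0.077 / √(0.3128/415) − 1.960) = 80.085%. The SAP's figure is reproduced.

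**2. The dropout allowance.**

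- 415 / (1 − 0.10) = 461.1, rounded up to 462.
- 462 − 415 = 47 per arm; 2 × 47 = 94. These also agree.

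**3. All 462 per arm analysed as allocated, at the SAP's own rates.**

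- Power = Φ(0.077 / √(0.3128/462) − 1.960) = 84.1%.
- With pooled variance, which is closer to the planned χ² test, it is 83.9%.

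Analysing more patients at the same rates raises power. Keeping everyone does not by itself take it below 80%.

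**4. What is needed to get below 80%.** An outcome has to be assumed for the 10%. With 462 per arm and unpooled variance:

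| Assumption about the 10% | Experimental | Control | Power |
|---|---|---|---|
| No dilution | 15.8% | 23.5% | 84.1% |
| Never have a fistula, both arms | 0.9 × 15.8 = 14.22% | 0.9 × 23.5 = 21.15% | 79.2% |
| Share a common rate of 19.65%, both arms | 16.18% | 23.11% | 75.8% |
| Have the control rate, experimental arm | 0.9 × 15.8 + 0.1 × 23.5 = 16.57% | 23.5% | 75.2% |
| Take the other arm's rate, both arms | 16.57% | 22.73% | 65.7% |
| All counted as fistulas, both arms | 24.22% | 31.15% | 65.6% |

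If only the experimental arm is diluted by patients at the control rate, power falls below 80% once they make up about 4.9% of that arm.

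The results run from about 66% to 84%. A band of 75 to 79% is one selection from that range, and the SAP states none of the assumptions in the table.

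**5. Dropouts with no observed outcome.** The expected number with an outcome is 0.9 × 462 = 415.8 per arm, which covers the required 415. If the loss is unrelated to outcome, the stated 80% holds. These patients could be kept in the comparison only by imputing a result.

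**6. The possible bias.** Suppose the excluded 10% had fistula risks of 40% (experimental) and 20% (control). A completers difference of −7.7 points would then be 0.9 × (−7.7) + 0.1 × (+20) = −4.9 points as randomised. The arithmetic is right, but neither risk comes from the document. The example shows what selective exclusion could do in principle and is no evidence about this trial.

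**The case for a change.** The strongest opposing case does not depend on any one power figure. The arm is revealed before the resection, and the whole analysis text is a χ² test, a t-test and a significance threshold. Analysis populations are ordinary SAP content. As written, an analyst could leave out randomised patients who did not receive the assigned anastomosis without contradicting the text. One sentence fixing analysis by allocated arm would cost nothing.

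Part of this stands. The SAP neither defines dropout nor names an analysis set, and a definition would be useful given when the envelope is opened. But silence is different from a rule that excludes patients. Nowhere does the SAP say that dropouts are patients who missed the allocated technique, that patients with a known outcome are removed, or that 415 is a per-protocol set. The protocol, which is not at hand, may define the population. Where nothing else is said, an analyst would normally compare patients by allocated arm.

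The dilution argument also needs two readings of dropout at once. The patients must be absent when the 80.085% is computed, yet present with known outcomes when the lower power is computed. The SAP commits to neither reading.

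**Conclusion.** The concern does not hold. The sample size, the stated power, the inflation to 462 per arm and the 94 expected dropouts are correct and agree with each other. Inflating by 1/(1 − 0.10) is standard for outcomes that are not observed, and it does not amount to a decision to discard randomised patients.

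Analysed as randomised at the SAP's rates, 462 per arm gives 84.1% power, about four points above the stated 80.085%. Lower values are conditional: 79.2% if the 10% never have a fistula, and 75.2% if that share of the experimental arm has the control rate. Writing such a range into the SAP as its power would present an assumption as a result. Calling 80.085% a per-protocol figure would give it a meaning the SAP does not.

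This conclusion rests on the SAP's planning rates and on reading dropout in its usual sense of an outcome not observed, with loss unrelated to outcome. The missing definitions of dropout and of the analysis set are a gap in detail that the protocol may fill. They are not an error in what the SAP states.

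### Does planning only a chi-square P-value for fistula leave the trial without an effect size or precision?

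*SAP*

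**What the plan says.** The analysis is described at the end of the sample-size paragraph in the opening text of the SAP. After naming SPSS version 20 it states "Variables were compared using the χ^2 test and independent samples t-test" and then "Differences were considered significant at a P -value of < 0.05". No effect measure, interval, regression model or covariate is named there or elsewhere in the document.

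The planning effect appears in the same paragraph, "Using clinically relevant pancreatic fistula of 23.5% in the control group and 15.8% in experimental group group", and again in the power output. Under Report Definitions, "D1 is the difference P1 - P2 assumed for power and sample size calculations"; the Numeric Results table gives its value as -0.0770. The Summary Statements add "The test statistic used is the two-sided Z-Test with unpooled variance" and "The significance level of the test is 0.0500".

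The analysis sentence speaks of variables in general and does not mention fistula. That fistula will be analysed by chi-square is an inference, but a safe one, because the endpoint is binary.

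**The concern.** The trial is sized to detect a difference between two proportions, yet nothing in the analysis text commits to estimating that difference. A P-value alone does not show whether a non-significant result is still compatible with the planned 7.7-point reduction, or whether a significant one rules out a trivial benefit. Surgeons deciding whether to choose the anastomosis by duct position need the size and the uncertainty of the reduction. If no measure is named in advance, the choice between risk difference, risk ratio and odds ratio is made after the data are seen.

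The comparison is also unadjusted, while the experimental strategy is built around one anatomical feature: the duct-position ratio, with its cut at 0.401.

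**Working it through.** **Inputs.** From the opening text and the Numeric Results table: p1 = 0.158 (experimental), p2 = 0.235 (control), two-sided alpha 0.05, power 0.80, 415 evaluable per arm. From the Dropout-Inflated Sample Size table: 10% dropout, 462 per arm.

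**The plan's own figures.**

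- Variance sum: 0.158 × 0.842 + 0.235 × 0.765 = 0.1330 + 0.1798 = 0.3128.
- Unpooled Z-test: n = 0.3128 × (1.960 + 0.842)² / 0.077² = 414.1, rounded up to 415.
- Power at 415: SE = √(0.3128/415) = 0.02745; Φ(0.077/0.02745 − 1.960) = 0.80085.
- Dropout: 415/0.90 = 461.1, rounded up to 462.

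All three stated figures are reproduced. The Pearson chi-square corresponds to the pooled-variance test. With pooled variance, power at 415 per arm is 0.798 and the requirement is 417, so planning with one form and testing with the other costs about 0.3 percentage points of power.

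**What the 2x2 table gives at the planned rates, 415 per arm.**

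- Risk difference: −7.7 points; half-width 1.96 × 0.02745 = 0.0538; 95% CI −13.1 to −2.3.
- Risk ratio: 0.158/0.235 = 0.67; SE of its log = √(0.842/(415 × 0.158) + 0.765/(415 × 0.235)) = 0.144; 95% CI 0.51 to 0.89.
- Odds ratio: 0.61; SE of its log = √(1/(415 × 0.133) + 1/(415 × 0.180)) = 0.178; 95% CI 0.43 to 0.87.
- Chi-square: the average rate is 0.1965, so z = 0.077/√(2 × 0.1965 × 0.8035/415) = 2.79; chi-square 7.79, P = 0.005.

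With all 462 per arm evaluable, the risk-difference interval is −12.8 to −2.6.

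**Smaller observed effects, control at 23.5%, 415 per arm.**

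- Smallest reduction reaching P < 0.05: about 5.5 points (18.0% against 23.5%), 95% CI for the reduction about 0.0 to 11.0.
- A 5-point reduction (18.5% against 23.5%): average rate 0.21, z = 0.05/√(2 × 0.21 × 0.79/415) = 1.77, P about 0.08. Half-width 1.96 × √((0.185 × 0.815 + 0.235 × 0.765)/415) = 0.0553, so the difference is −5.0 points with 95% CI −10.5 to +0.5.

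The second interval contains both zero and −7.7, so in that case the interval is clearly more informative than the P-value. In each case, however, it needs only the two event counts and the two denominators, which the chi-square already uses.

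**Adjustment.** The opening text says the envelopes are opened in the operating room before the resection, and describes the duct and thickness measurements as made during surgery in the experimental group. It mentions no stratification of the randomization and no measurement of the ratio in controls. A Mantel-Haenszel estimate stratified at 0.401 would need that control measurement. The gain in precision cannot be calculated, because the SAP gives no fistula rates by duct position.

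**The case for a change.** The strongest argument for a change is that naming the effect measure and its interval is core SAP content and cannot simply be left to a protocol. The SAP does set out its analysis, and what it sets out is tests and a threshold. The calculations show that a 5.5-point result with an interval touching zero and the planned 7.7-point result with an interval of 2.3 to 13.1 would both be called significant. One sentence would cure this at no cost in patients.

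Much of that stands. A fuller SAP would name the measure, and a report giving the risk difference with its 95% CI beside the P-value would be better than one without. What does not stand is that the trial as planned cannot provide these. The SAP does not restrict reporting to P-values, and it gives no rule for describing a non-significant result, so nothing in it says that a 5-point reduction would be presented as no difference. Observed rates can be set directly against 15.8% and 23.5%. Choosing the summary measure later cannot move the significance verdict, which the chi-square fixes; any reader with the counts can compute all three measures.

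The adjustment argument is weaker. An unadjusted comparison of randomized arms is unbiased, and no stated design factor calls for adjustment. A stratum recorded in the operating room once the allocation is known could be measured, or be missing, differently between arms. The simple comparison avoids that risk.

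**Conclusion.** No change to the plan follows. The omission is real: the SAP names no effect measure or interval. It is a reporting detail that analysts routinely supply, and the chi-square test is valid for the powered hypothesis of no difference in proportions. The risk difference and its interval come from the same table, with a half-width of about 5.4 points at the planned rates and 415 per arm. For variables compared by t-test, the mean difference and its interval likewise come from the means, standard deviations and group sizes used in the test. The sample size of 415 evaluable and 462 enrolled per arm is unaffected. The lack of adjustment for duct position is not an error.

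This rests on three assumptions: that fistula is the variable analysed by chi-square, that event counts and denominators are reported by arm, and that the rates are near those assumed in planning. The protocol was not available here and may already name the measure; the conclusion does not depend on that.

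### Does a single P < 0.05 rule for all variables leave the trial without an identified confirmatory comparison?

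*SAP*

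**What the plan says.** The second paragraph of the SAP holds the whole analysis text. It states that "Variables were compared using the χ^2 test and independent samples t-test" and that "Differences were considered significant at a P -value of < 0.05". Neither sentence names an endpoint or a contrast. The words primary, secondary, confirmatory and exploratory appear nowhere in the SAP, and there is no statement on multiplicity.

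The rest of the document is more specific:

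- The title names postoperative pancreatic fistula as the outcome of interest.
- The opening paragraph sets up two randomised arms: "The participants were randomly divided into the experimental group and the control group".
- The sample-size text takes one endpoint and one contrast: "Using clinically relevant pancreatic fistula of 23.5% in the control group and 15.8% in experimental group group".
- Under Tests for Two Proportions, one pair of hypotheses is given: "H0: P1 - P2 = 0. H1: P1 - P2 = D1 ≠ 0".
- Report Definitions identifies group 1 as the experimental group and group 2 as the control group.
- Summary Statements says of this comparison that "The test statistic used is the two-sided Z-Test with unpooled variance" and that "The significance level of the test is 0.0500".

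**The concern.** Read alone, the two analysis sentences look open-ended. The 0.05 threshold is attached to no endpoint, and the t-test cannot be the test of a fistula proportion. At least one other variable must therefore fall under the same rule. The statistic used for sizing (unpooled Z) is not the one named for analysis (χ²), so no sentence expressly links the sized hypothesis to its test. The experimental arm is also divided by duct position into groups called N1 and N2, the symbols that the power table uses for the two arm sizes.

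If several results could each be claimed as the trial's finding at 5%, the chance of at least one false claim would exceed 5%, and the result that decides the trial could be chosen after the data are seen.

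**Working it through.** **1. Reproduce the sized test.** The inputs are in the second paragraph and the power table: p1 = 0.158 (experimental), p2 = 0.235 (control), d = 0.077, two-sided α = 0.05, power 80%, unpooled variance.

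- p1(1 − p1) + p2(1 − p2) = 0.158 × 0.842 + 0.235 × 0.765 = 0.133036 + 0.179775 = 0.312811.
- n per arm = (1.960 + 0.842)² × 0.312811 / 0.077² = 414.10 (unrounded normal quantiles), rounded up to 415. The SAP gives 415.
- SE at 415 = √(0.312811 / 415) = 0.02745. Power = Φ(0.077 / 0.02745 − 1.960) = 0.80085. The SAP gives 0.80085.
- Dropout of 10%: 415 / 0.90 = 461.1, rounded up to 462. The SAP gives 462, or 924 in total.

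The calculation spends the full 0.05 on one test, and that test compares whole arms. The N1 and N2 of the power table are arm sizes, as Report Definitions says. They are not the duct-position groups.

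**2. Count the hypotheses that the SAP states.**

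| Element | Endpoint or contrast named |
|---|---|
| Title | Postoperative pancreatic fistula |
| Randomisation | Experimental vs control |
| Sample-size text | Clinically relevant pancreatic fistula, experimental vs control |
| Tests for Two Proportions | One H0/H1 pair |
| Summary Statements | The same pair, at 0.0500 |
| Analysis sentences | None named |

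There is one endpoint, one contrast and one hypothesis. No continuous outcome is named, and no comparison of the duct-position groups is scheduled; those groups only determine which anastomosis is performed.

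**3. Does Z versus χ² break the link?** Both test equality of two proportions, and the Pearson χ² without continuity correction is the square of the pooled Z. At 415 per arm:

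- unpooled Z: power 0.8008;
- χ² (pooled): pooled proportion (0.158 + 0.235) / 2 = 0.1965; power = Φ[(0.077 × √415 − 1.960 × √(2 × 0.1965 × 0.8035)) / √0.312811] = 0.7983.

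The difference is 0.0025, and the pooled formula asks for 417 per arm instead of 415. Fistula is the only proportion with a stated hypothesis and χ² is the only test for proportions named, so the reader can match them.

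**4. What error rates are at stake?** With the one stated hypothesis, the error is 5% by design. Exact binomial enumeration at 415 per arm with both rates at 0.235 gives 0.0502 for the χ² test. Anything higher needs an assumption that the SAP does not supply:

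| Assumed additional testing, all counted as confirmatory | Chance of at least one false claim |
|---|---|
| None (as stated) | 5.0% |
| One further variable, independent: 1 − 0.95² | 9.75% |
| One further variable, correlation 0.5 / 0.9 | 9.1% / 7.0% |
| Overall fistula test plus one three-group χ² | 7.5% |
| Overall fistula test plus each duct group vs control | 10.3–10.4% |
| The same, plus one duct group vs the other | 12.6–13.1% |

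The correlations are assumed. The duct-group rows assume a central-duct share of 20–80%. Each row below the first describes a different plan from the one written.

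**The case for a change.** The best opposing argument is that a sample-size calculation does not limit what may later be called significant. The sentence that sets the significance rule has no limit of scope, and the t-test shows that it reaches beyond fistula. One added sentence would close the question at no cost, and it is worth most before results are known.

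Part of this stands. The SAP carries no explicit primary or confirmatory label and no multiplicity statement, and such a sentence would be harmless. The step from there to a defect fails for three reasons.

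- A nominal 0.05 threshold is a convention for reporting P-values. It does not say that every variable crossing it is a confirmatory claim.
- The t-test shows only that some continuous variable is compared. That could be a baseline characteristic, in which case there is no second outcome test at all.
- Naming the primary endpoint and ranking the others commonly belongs to the protocol, which is not available. Its absence from the SAP therefore does not show that the plan lacks it.

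**Conclusion.** The concern does not hold. In substance the SAP already singles out the comparison that decides the trial: clinically relevant pancreatic fistula, all experimental against all control patients, two-sided 0.05. Carried out as written, with the χ² test, the plan gives a valid answer to that question with a type I error of about 5% and power of about 80%. No inflation of the error rate can be shown, because the SAP states no second confirmatory test. Adding a label would change neither the 415 evaluable nor the 462 enrolled per arm, nor the alpha, nor the analysis.

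The conclusion rests on two assumptions. The first is that χ² means the Pearson test without continuity correction; the corrected formula would ask for 443 per arm, but that bears on power and not on which comparison is decisive. The second is that the protocol names no competing primary endpoint; nothing in the SAP suggests one.
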